## **5 STUDY OBJECTIVES**

### **5.1 PRIMARY**

The primary objective is to evaluate long-term safety of alemtuzumab.

### **5.2 SECONDARY**

The secondary objectives are:

- To evaluate long term efficacy of alemtuzumab.
- To evaluate the safety profile of patients who received other DMT following alemtuzumab treatment.
- To evaluate patient-reported quality of life (QoL) outcomes and health resource utilization of patients who received alemtuzumab.
- To evaluate as needed re-treatment with alemtuzumab and other DMTs.

## 6 STUDY DESIGN

### 6.1 DESCRIPTION OF THE PROTOCOL

This study is a Phase 3B/4, international, multicenter, open-label, non-comparative study to evaluate the long-term safety, efficacy and QoL of alemtuzumab in patients who have completed at least 48 months of the extension study CAMMS03409. In addition, impact of treatment on pharmaco-economic data will be evaluated.

Patients treated with alemtuzumab within 48 months prior to enrollment in the LPS13649 study must be followed-up at monthly intervals until 48 months after the last infusion of alemtuzumab ([Section 10.1.6.2](#)).

Scheduled visits for safety and efficacy assessments will be performed every six months. AEs and concomitant medications will be monitored continuously. Quality of life, pharmaco-economic data and brain imaging will be collected every twelve months.

Patients must contact the treating neurologist at the study site (Study Investigator) as soon as they experience any sign or symptom of MS relapse. The Study Investigator will decide on the need to schedule extra visits (unscheduled visits) to evaluate the patient's status. All procedures and assessments will be collected in the e-CRF.

At the Study Investigator discretion patients can be treated:

- Patients may receive additional courses of alemtuzumab but not sooner than 12 months from any previous alemtuzumab treatment course, or
- Patients may receive other commercial DMTs.

In the event that a Study Investigator decides to treat a patient (with alemtuzumab or another DMT) the factors contributing to the decision to treat (eg, patient is experiencing clinical and/or imaging activity) should be documented in the e-CRF.

For treatment courses of alemtuzumab the Study Investigator should refer to the safety information in the Investigator's Brochure (IB) or in the approved label in the country/region when available. All treatment courses will consist of 12 mg/day alemtuzumab intravenously infused once daily on 3 days ([Section 8.1](#)).

If the patient is re-treated with additional courses of alemtuzumab, the patient will be followed using the specific recommendations indicated in the IB or in the local approved label (when available). Patients will be followed for 48-months after the last infusion of alemtuzumab received in the current trial setting. During the 48-month period, laboratory safety sampling should be collected every month, in a local laboratory and they must be reviewed in a timely manner by the Study Investigator.

If the 48-month period of required safety follow-up continues after the study ends, the patient will be followed by their physician in a regular healthcare setting, in line with the local approved Risk Minimization Plan for alemtuzumab, until the 48-month period is completed.

A pharmacogenomics (PGx) substudy will be conducted for exploratory analysis of genetic variations predictive of autoimmune conditions, including thyroid disorders and immune thrombocytopenia (ITP), related to MS disease and/or the effects of alemtuzumab. Objectives of the substudy are as follows:

- To develop biomarkers predictive of autoimmune conditions including thyroid disorders and immune thrombocytopenia. This will include collection of samples from patients who have not yet developed any auto immune conditions; these samples would be used as controls.
- To explore efficacy and safety markers through data analysis.
- To explore genetic variation related to MS disease manifestation through data analysis.

For research purposes only and on a voluntary basis, a blood sample will be collected from approximately 300 ongoing patients who signed the optional pharmacogenomic informed consent form and who have not previously provided a PGx sample. Details of the PGx substudy are presented in [Appendix C](#), “Exploratory Pharmacogenomics Assessment Substudy”.

## **6.2 DURATION OF STUDY PARTICIPATION**

### **6.2.1 Duration of study participation**

Study duration will be 5 years (plus a window of 6 months) from the day of the enrollment of the first patient.

### **6.2.2 Determination of end of clinical trial (all patients)**

The end of the clinical trial occurs 5 years (plus a window of 6 months) after the inclusion of the first patient.

## **6.3 INTERIM ANALYSIS**

No interim analysis is planned; an annual partial database lock will be made available for publication purpose.

## **6.4 STUDY COMMITTEES**

No study committees are planned.

## **7 SELECTION OF PATIENTS**

### **7.1 INCLUSION CRITERIA**

- I 01. Patient has completed at least 48 months of the Extension Study CAMMS03409.
- I 02. Signed written informed consent form (ICF).

### **7.2 EXCLUSION CRITERIA**

- E 01. Patient participating in another investigational interventional study.

## 8 STUDY TREATMENTS

### 8.1 INVESTIGATIONAL MEDICINAL PRODUCT(S)

Name of the Investigational Medical Product (IMP):

- Alemtuzumab.

Pharmaceutical form:

- Concentrate for solution for infusion (sterile concentrate).

Dose of drug per administration:

- 12 mg/day on 3 consecutive days (36 mg total dose).
- Missed doses should not be given on the same day as a scheduled dose.

Route of administration:

- Intravenous infusion.

#### 8.1.1 Administration

There is no fixed treatment requirement or schedule. Administration of alemtuzumab will only be done following a decision from the Study Investigator that an additional “as needed” course is indicated.

Alemtuzumab will be then administered by IV infusions in a supervised medical setting at a dose of 12 mg/day on 3 consecutive days (36 mg total dose) at least 12 months after the prior treatment course.

##### 8.1.1.1 Method of preparation at the clinical site

Alemtuzumab must be diluted before infusion. The diluted solution should be administered by intravenous infusion over a period of approximately 4 hours.

##### 8.1.1.2 Special precautions for disposal and other handling

The vial contents should be inspected for particulate matter and discoloration prior to administration. Do not use if particulate matter is present or the concentrate is discolored. Do not shake the vials prior to use.

For intravenous administration, withdraw 1.2 mL of alemtuzumab from the vial into a syringe using aseptic technique. Inject into 100 mL of sodium chloride 9 mg/mL (0.9%) solution for infusion or glucose (5%) solution for infusion. This medicinal product must not be diluted with other solvents. The bag should be inverted gently to mix the solution.

Alemtuzumab contains no antimicrobial preservatives and, therefore, care should be taken to ensure the sterility of the prepared solution. It is recommended that the diluted product be administered immediately. Each vial is intended for single use only.

Any unused medicinal product or waste material should be disposed of in accordance with local requirements.

### **8.1.2 Pre-treatment**

All the specific recommendations indicated in the IB or in the local approved label (when available) should be checked before starting the re-treatment with alemtuzumab. Physician should also consider the contraindications of alemtuzumab when re-treating patient in this study ([Section 10.1.6.1](#)).

Patients should be pre-treated with corticosteroids (eg, 1000 mg methylprednisolone IV) immediately prior to alemtuzumab administration on each of the 3 days of treatment.

Additionally, pretreatment with antihistamines and/or antipyretics prior to alemtuzumab administration may also be considered.

Oral prophylaxis for herpes infection should be administered to all patients starting on the first day of treatment and continuing for a minimum of 1 month following treatment with alemtuzumab. The choice of the therapy and the dose will be at the discretion of the Study Investigator.

### **8.1.3 Post-treatment**

Observation for infusion associated reactions is recommended during and for a minimum of 2 hours after alemtuzumab infusion.

Patients treated with alemtuzumab must commit to 48-months of follow-up after the last infusion. It is possible that this period continues after study completion, in a regular healthcare setting.

## **8.2 NONINVESTIGATIONAL MEDICINAL PRODUCT(S)**

Not applicable.

## **8.3 BLINDING PROCEDURES**

No blinding procedures are planned.

## **8.4 METHOD OF ASSIGNING PATIENTS TO TREATMENT GROUP**

No method of assigning patients to treatment group is planned.

## **8.5 PACKAGING AND LABELING**

The content of the labeling is in accordance with the local regulatory specifications and requirements.

Alemtuzumab will be packaged in 3-vial cartons. Each vial contains 12 mg of alemtuzumab per 1.2 mL of solution. The vials are single use only and contain no preservatives. The label text for the alemtuzumab vial will, at a minimum, include the protocol number, the contents of the vial (ie, alemtuzumab 10 mg/mL, 1.2 mL vial), lot number, appropriate cautionary statements, route of administration, storage conditions, and name and address of Genzyme (a Sanofi company). Labels comply with Good Manufacturing Practices and national legislation.

## **8.6 STORAGE CONDITIONS AND SHELF LIFE**

Alemtuzumab, in vials, should be stored at 2° to 8°C (36 to 46°F). Do not freeze. Do not use alemtuzumab beyond the use by date provided on the label or other documentation. Protect from light.

Alemtuzumab diluted product may be stored at room temperature (15° to 25°C) or refrigerated conditions (2° to 8°C), and should be used within 8 hours after dilution. From a microbiological point of view, it is recommended that the product should be used immediately. Protect from light. Partially used, unused, or damaged drug vials should be disposed according to institutional policies.

Alemtuzumab will be used in accordance with the approved protocol and must not be used for any other purpose.

## **8.7 RESPONSIBILITIES**

The Study Investigator, the hospital pharmacist, or other personnel allowed to store and dispense the IMP will be responsible for ensuring that the IMP used in the clinical trial is securely maintained as specified by the Sponsor and in accordance with applicable regulatory requirements.

All IMP will be dispensed in accordance with the Study Investigator's prescription and it is the Investigator's responsibility to ensure that an accurate record of IMP issued and returned is maintained.

Any quality issue noticed with the receipt or use of an IMP (deficiency in condition, appearance, pertaining documentation, labeling, expiration date, etc) should be promptly notified to the Sponsor. Some deficiencies may be recorded through a complaint procedure.

A potential defect in the quality of IMP may be subject to initiation of a recall procedure by the Sponsor. In this case, the Study Investigator will be responsible for promptly addressing any request made by the Sponsor, in order to recall IMP and eliminate potential hazards.

Under no circumstances will the Study Investigator supply IMP to a third party, allow the IMP to be used other than as directed by this clinical trial protocol, or dispose of IMP in any other manner.

### **8.7.1 Treatment accountability and compliance**

As alemtuzumab will be administered by daily IV infusions in a supervised medical setting, on an outpatient basis, by qualified center personnel, responsibility for compliance with mandatory safety assessments resides with the Study Investigator.

### **8.7.2 Return and/or destruction of treatments**

The Study Investigator will not destroy the unused IMP unless the Sponsor provides written authorization. A detailed treatment log of the destroyed IMP will be established with the Study Investigator (or the pharmacist) and countersigned by the Study Investigator and the monitoring team.

## **8.8 CONCOMITANT MEDICATION**

A concomitant medication is any treatment received by the patient concomitantly to any IMP(s). In the current study, all medications received by the patient from the end of the Extension Study CAMMS03409 to Visit 1 of LPS13649 study, and during the study until the last visit will be collected.

Patients who need to be re-treated with alemtuzumab and who are receiving treatment with other DMTs, should discontinue the other DMTs according to their local approved label. The potential for additive effects on the patient's immune system must be taken into account. Concomitant use of alemtuzumab with some therapies could increase the risk of immunosuppression.

### **8.8.1 Forbidden concomitant medications**

Patients should not receive live vaccines 6 weeks prior to alemtuzumab administration or during the study.

All the specific recommendations indicated in the IB or in the local approved label (when available) should be checked before starting the re-treatment with alemtuzumab.

## 9 ASSESSMENT OF INVESTIGATIONAL MEDICINAL PRODUCT

### 9.1 PRIMARY ENDPOINTS: SAFETY

Safety assessments will include the following:

- Incidence, duration, grade/intensity, relationship to study drug, and outcome of the following:
  - Serious Adverse Events (SAEs).
  - Adverse Events (AEs).
  - Infusion-associated reactions (IAR).
- Incidence, nature, seriousness, grade/intensity, relationship to study drug, and outcome of the following project-specific Adverse Events of Special Interest (AESIs):
  - Autoimmune mediated conditions including, but not limited to:
    - Immune thrombocytopenic purpura (ITP).
    - Nephropathies including anti-glomerular basement membrane (GBM) disease.
    - Cytopenias.
    - Thyroid disorders.
    - Acquired hemophilia A
    - Autoimmune hepatitis.
    - Hemophagocytic lymphohistiocytosis (HLH).
    - Progressive multifocal leukoencephalopathy (PML)
    - Temporally associated\* pulmonary alveolar hemorrhage
    - Temporally associated\* myocardial ischemia, myocardial infarction
    - Temporally associated\* stroke
    - Temporally associated\* cervicocephalic arterial dissection(\* Temporally associated: 1 to 3 days after the last infusion)
  - Serious infections including serious opportunistic infections (eg, Listeria infections, CMV, EBV), HPV associated with cervical dysplasia
  - Malignancy.
  - Pneumonitis
- Changes in laboratory parameters.

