Identified risks of alemtuzumab in patients with MS include:

- Infusion-associated reactions (IAR)
- Serious infections
- Autoimmunity (notably, Immune thrombocytopenic purpura (ITP), thyroid dysfunction and nephropathies)

The most important adverse reactions are autoimmunity (eg, ITP, thyroid disorders, nephropathies, cytopenias), IARs, and serious infections. The most common adverse events

reported after alemtuzumab treatment (in  $\geq 20\%$  of patients) are rash, headache, pyrexia, and respiratory tract infections. Of note, Listeriosis/Listeria meningitis has been reported in LEMTRADA treated patients, generally within one month of LEMTRADA infusion. To reduce the risk of infection, patients receiving LEMTRADA should avoid ingestion of uncooked or undercooked meats, soft cheeses and unpasteurized dairy products two weeks prior to, during, and for at least one month after LEMTRADA infusion.

The Sponsor has conducted a comprehensive review of safety data from post-marketing use of alemtuzumab and added the following to the current list of AESIs:

- Autoimmune hepatitis
- Acquired hemophilia A
- Hemophagocytic lymphohistiocytosis (HLH)
- Progressive multifocal leukoencephalopathy (PML)
- Temporally associated\* pulmonary alveolar hemorrhage
- Temporally associated\* myocardial ischemia, myocardial infarction
- Temporally associated\* stroke
- Temporally associated\* cervicocephalic arterial dissection

\* Temporally associated: 1 to 3 days after the last infusion

Cases of serious and life-threatening stroke (including hemorrhagic and ischemic), myocardial infarction and cervicocephalic (ie, vertebral, carotid) arterial dissection have been reported within three days of alemtuzumab administration, with most cases occurring within one day. Cases of pulmonary alveolar hemorrhage have been reported with onset within 48 hours of alemtuzumab infusion. Long term auto immune risks, such as cases of Hemophagocytic lymphohistiocytosis (HLH) and autoimmune hepatitis causing clinically significant liver injury, including acute liver failure requiring transplant, has been reported. To minimize the risk of these serious adverse events, recommendations are provided for infusion related management and long term safety monitoring for patients receiving re-treatment of alemtuzumab during the course of the trial:

- Pre infusion: assess overall health status and risk factors; baseline BP/HR, bleeding risk, platelets count. Baseline liver function test.

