  - Temporally associated\* cervicocephalic arterial dissection  
(\* Temporally associated: 1 to 3 days after the last infusion)
  - Serious infections including serious opportunistic infections (eg, Listeria infections, CMV, EBV), HPV associated with cervical dysplasia
  - Malignancy.
  - Pneumonitis

The standardized MedDRA queries (SMQ) or Custom MedDRA queries (CMQ) will be applied as appropriate to select AESIs.

**Infusion-associated reactions (IAR)** is defined as any adverse event occurring during and within 24 hours of alemtuzumab infusion. It will be analyzed separately for retreated patients.

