### ***Analysis of adverse events of special interest (AESI)***

- All treatment-emergent adverse events of special interest by primary SOC, HLG, HLT, and PT, showing the number (%) of patients sorted by the internationally agreed SOC order. The other levels (HLG, HLT, PT) will be presented in alphabetical order
- All treatment-emergent adverse events of special interest by primary SOC and PT, showing the number (%) of patients with at least 1 treatment-emergent adverse event, sorted by the internationally agreed SOC order and by decreasing incidence of PTs within each SOC. This sorting order will be applied to all other tables, unless otherwise specified
- All treatment emergent adverse events of special interest by PT, showing the number (%) of patients, sorted by decreasing incidence of PT
- The event rate per patient-year (the number of events in question divided by total treatment exposure in patient years) for non-temporary AESI(s) will be provided by SOC and PT
- The frequency of treatment-emergent adverse events over time will be provided for the non-temporary treatment-emergent AESIs, where the time intervals will be defined as: <2 courses, 2 – 4 courses, 4 – 6 courses, 6 – 8 courses, etc. In each time interval, the denominator for calculation of percentage will be the number of patients who entered the time interval and the numerator will be the number of patients with at least 1 treatment emergent AESI occurring in this time interval. Note that only the first event will be counted and all recurrent events will not be included
- For retreated population, the frequency of treatment-emergent temporary adverse events over time will be provided for the temporally associated AESIs (pulmonary alveolar hemorrhage, myocardial ischemia, myocardial infarction, stroke, cervicocephalic arterial dissection), where the time intervals will be defined as: during alemtuzumab infusion day 1, during alemtuzumab infusion day 2, during alemtuzumab infusion day 3, 1 day after alemtuzumab infusion, 2 days after alemtuzumab infusion and 3 days after alemtuzumab infusion. In each time interval, the denominator for calculation of percentage will be the number of patients who entered the time interval and the numerator will be the number of patients with at least 1 treatment emergent AESI occurring in this time interval. Note that only the first event will be counted and all recurrent events will not be included

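### The SAP defines temporally associated AESIs by a window after the last infusion, then tabulates the same AESIs on the infusion days, which the plain reading of that window excludes

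*Protocol*

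**What the plan says.** Protocol Section 9.1 makes AESI incidence part of the primary safety endpoint. Four entries (pulmonary alveolar hemorrhage, myocardial ischemia or infarction, stroke, and cervicocephalic arterial dissection) carry this footnote: "Temporally associated: 1 to 3 days after the last infusion". It also stands in the Clinical Trial Summary, Section 4, Section 10.4.1.3, Table 2 of Section 10.4.4, and SAP 2.1.4.1.

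On selecting events, SAP 2.1.4.1 says: "The standardized MedDRA queries (SMQ) or Custom MedDRA queries (CMQ) will be applied as appropriate to select AESIs".

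For re-treated patients, SAP 2.4.5.1 says that "the frequency of treatment-emergent temporary adverse events over time will be provided for the temporally associated AESIs". The rows are "during alemtuzumab infusion day 1, during alemtuzumab infusion day 2, during alemtuzumab infusion day 3, 1 day after alemtuzumab infusion", then "2 days after alemtuzumab infusion and 3 days after alemtuzumab infusion". In each row, "the numerator will be the number of patients with at least 1 treatment emergent AESI occurring in this time interval".

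Protocol Section 8.1 sets a course of infusions on three consecutive days and foresees interruptions: "Missed doses should not be given on the same day as a scheduled dose". Section 4 says of earlier stroke, infarction and dissection cases that they "have been reported within three days of alemtuzumab administration, with most cases occurring within one day".

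**The concern.** The table and the definition concern the same events but cover different days, and both stand in the SAP. A programmer has two courses open, and each goes wrong.

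- **Apply the footnote as a filter.** On its plain reading, an event on an infusion day is not an AESI. The infusion-day rows then show zero whatever happened, and a reader may take this as evidence of safety. Section 4 does not contradict the footnote, but it shows that onset on or close to an infusion day is expected. Section 10.1.6 likewise names these events in its instructions for the infusion itself.
- **Apply only the MedDRA query.** A query selects by term, not by onset time. A stroke or infarction long after any infusion could then enter the general AESI tables under a temporally associated label, even in a patient never re-treated in this study. The SAP's separate summaries for non-temporary AESIs rest on the same unstated split.

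The footnote also governs reporting. Under Sections 10.4.1.3 and 10.4.4, AESI status triggers notification within 24 hours even for a non-serious event.

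**Working it through.** The plan gives no figure to reproduce, so the check is an enumeration.

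**Inputs.** Infusions fall on calendar days 1, 2 and 3 (Protocol 8.1). The six SAP rows are then onset days 1 to 6: infusion days 1, 2, 3, and +1, +2, +3 counted from the third infusion. A row is covered if onset on that day meets the footnote.

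**Step 1: calendar-day readings of the footnote.**

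| *Last* means | Infusion day is | Onset days covered | Rows of 6 |
|---|---|---|---|
| Final of course | day 0 | 3+1 to 3+3 = 4 to 6 | 3 |
| Final of course | day 1 | 3+0 to 3+2 = 3 to 5 | 3 |
| Most recent | day 0 | 4 to 6 if onset follows that day's infusion; 2 to 6 if it precedes it | 3 to 5 |
| Most recent | day 1 | 1 to 5 if onset follows that day's infusion; 2 to 5 if it precedes it | 4 to 5 |
| Any infusion | day 0 | 2 to 6 | 5 |
| Any infusion | day 1 | 1 to 5 | 5 |

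The first line is the plain reading. It leaves 6 − 3 = 3 rows empty, and these are the three infusion days.

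**Step 2: 24-hour periods from the most recent infusion.** Assume a 10:00 start; Protocol 8.1.1.1 gives about 4 hours of infusion, so each ends at 14:00. Take *after* to mean after the infusion has ended, with the first 24 hours as day 1. The window is 3 × 24 = 72 hours. Infusions end 24 hours apart, so coverage runs without a break from 14:00 on day 1 to 14:00 on day 6. Days 2 to 5 are fully covered, and days 1 and 6 in part. All six rows can hold events, but onset during the first infusion (10:00 to 14:00 on day 1) stays outside.

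**Step 3: the post-infusion rows.** SAP 2.4.5.1 does not name the infusion from which its last three rows count. Anchored to the final infusion, each onset day falls in exactly one row. With no anchor, onset days 2, 3, 4 and 5 each fit more than one row; day 4, for example, is 1, 2 and 3 days after the third, second and first infusions.

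**Step 4: a window that fits the six rows.** Take onset from the start of the first infusion through calendar day +3 after the final infusion given, that day being day 0. With k consecutive infusions there are k + 3 rows, all covered: 6 of 6, 5 of 5 and 4 of 4 for k = 3, 2 and 1. This is a consistency check only, because the window was built from the rows. If a day is skipped (infusions on days 1, 2 and 4, say), onset on day 3 has no row, so an extra row is needed.

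**The case against.** The strongest reply is that this is a loose footnote, not a broken analysis. Three stronger claims that a reader might infer do fail.

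- *Neither text gives an anchor or a range.* The footnote gives both: the last infusion, and 1 to 3 days. What is open is whether *last* means final or most recent, and where the count starts. Only SAP 2.4.5.1 names no anchor infusion.
- *No reading of the footnote can match the table.* Step 2 shows one under which every row can hold events, and it sits well with the timing described in Section 4. It still leaves out onset during the first infusion unless *after* is counted from the infusion's start, which the documents do not say.
- *Most onset days are ambiguous in the table.* The rows form one ordered list, infusion days first, and read naturally as anchored to the final infusion. On that reading no day is ambiguous.

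The reply is also right that little is lost. Infusion-day events remain adverse events, are infusion-associated reactions if they occur during or within 24 hours of infusion (Section 9.5.1), and are SAEs if serious. Table 2 gives SAEs the same 24-hour route whether or not they are AESIs. The SAE listing shows onset date and study day. A late stroke cannot enter the six-row table, which ends 3 days after infusion.

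What stands is that the plain reading contradicts the table, and that the SAP does not choose another reading or place the window relative to term selection.

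**Conclusion.** SAP 2.1.4.1 and 2.4.5.1 need to be reconciled. On the plain reading, three of six rows are empty by definition and infusion-day onsets drop out of an AESI count that belongs to the primary endpoint. Other calendar-day readings cover 3 to 5 rows. The 24-hour reading reaches all six but omits onset during the first infusion. These counts assume infusions on three consecutive days; the 24-hour result also assumes the start time above and counting from the end of infusion.

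The consequence is limited to descriptive AESI tables and to expedited notification of non-serious infusion-day cases. SAP 2.4.5 plans no systematic testing of safety variables, so no test result changes. The number of events affected cannot be computed. The documents do not settle which window was intended, so it would go too far to conclude that the footnote is the error and the table is right.

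**What to change.** Reconcile SAP 2.1.4.1 and 2.4.5.1 to one onset window that states the anchor infusion and the day numbering, and state that it is applied after SMQ/CMQ term selection.

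If the six rows are kept, the matching analysis window is: onset from the start of the first infusion of a course through calendar day +3 after the final infusion actually given in that course, the day of that infusion being day 0. Define the rows by calendar day, anchor the three post-infusion rows to that same infusion, and add a row for any non-infusion day between infusions.

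Record the change in SAP 1.5, now marked not applicable, as a departure from the protocol footnote. Align the five protocol footnotes at the next amendment, since they set the investigator's AESI reporting duty; Section 15 requires IRB/IEC approval.

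The cost is wording in two analysis sections and an entry in SAP 1.5, with no new data. The AESI count may rise, and the SAP and protocol wording will differ until the amendment. Keeping the footnote on its plain reading and deleting the three infusion-day rows would also remove the conflict, without an amendment. It would leave infusion-day onsets outside the AESI count, visible only as AEs, infusion-associated reactions or SAEs.
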